Presenting risk clearly, with specific formats, and talking through the issues can help to improve patient understanding. Health literacy related oral communication techniques, such as the teach-back method, can help the educator confirm understanding and enhance clinical outcomes [59]. Because of difficulty in communicating risk, and the infrequency of optimal communication strategies in usual care, our experienced investigator team will carefully construct content and nuances of risk communication and training and protocols for educators to use best practices, such as active listening and the teach-back. Our team includes experts in health literacy ([name]) and disparities communication (Drs. [name], [name], and [name]) and we have extensive experience developing successful, culturally sensitive risk communication [96-100, 13]. We will ensure that short term consequences and cure rates are well understood and one year mortality information is clearly described with and without surgery. The communicator will “close the loop” at **multiple points over time** to ensure patient comprehension. If surgical decisions don’t fit prognosis, we will use alternative methods to convey information such as narratives or story telling [101]. As a key component of intervention development, we will test comprehension of our message and acceptability of communication techniques using individual patient interviews prior to the randomization phase. We will use the interviews iteratively to develop the intervention techniques and include people with low health literacy and low numeracy. These interviews will be taped (with consent) for fidelity of factual information and delivery techniques, and the CCE will be given feedback based on the tapes. After the final tools are developed, the CCE will use the lung cancer algorithms and teach-back confirmation with all participants *who are randomized to the CCE intervention. The CCE will have a face to face sessions at initial diagnosis and one 10 to 14 days after diagnosis.* More visits will be scheduled if the CCE cannot confirm patient understanding of risk and prognosis. *The CCE will re-engage any individual who is randomized to the patient intervention and who drops out of care as defined by a lack of follow-up appointment within a month of the index visit, failure to schedule surgery when recommended, or a missed appointment for follow-up or procedures. The CCE will inform the designated site physician champion about direct recommendations against surgery if no absolute contra-indications are defined in the record. The physician champion will arrange clinical evaluations as noted below. Patients in the intervention group will be encouraged to initiate contact with the CCE when questions or concerns occur.*

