
B. Data Feedback – Results of the retrospective chart review will be distributed to and reviewed with all lung cancer care providers at their participating institutions. Particular emphasis will be placed on the role of co-morbid conditions and outcomes according to race (VII). Since small clusters of physicians perform nearly all lung cancer care in each health system, cross-contamination for any physician-specific intervention is very likely. Therefore, prospective physician feedback will be delivered at all institutional sites. Cumulative data feedback that includes race, co-morbidity variables and surgical rates will be presented to lung cancer providers *by an identified physician champion at each clinical site* quarterly. “Drop outs” and negative provider recommendations will be flagged in real time. The clinic champion will arrange intensive clinical review if the barrier stems from clinical recommendations while the CCE will re-examine patient related barriers. Current IT systems at cancer care organizations do not often factor in patient race, track “real time” clinical performance, generate regular provider reports or suggest options for improvement (V). Although routine quality improvement has not always been effective in addressing disparities [28], we will create a race-specific registry for our study patients similar to the effective registry that Bickell et al. [16] employed for adjuvant breast cancer therapies. We will follow the effect of the registry function via historical controls.

- C. Registry development – note that [name] and [name] have past experience designing a diabetes registry with care flags and point of care reminders that is utilized for paper-based practices in a statewide quality improvement project (formally IPIP, now the North Carolina Healthcare Quality Alliance). The same electronic backbone will be used to track appointments, procedures, adherence and recommendations related to care for early stage, non-small cell, lung cancer.

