- D. Co-morbidity educational checklist – The co-morbidity check list will be designed to address the seeming over interpretation of co-morbid states in decisions against surgery by African-American patients or their physicians (II and VII). Derived from the retrospective chart review, this checklist will be used to help inform physicians' decisions in patients who do not have absolute contra-indications for surgery. Overall results of the retrospective chart review will be delivered at the beginning of designated MTOP conferences at each study site or at a mutually agreeable meeting that includes the whole lung cancer care team. For African-American study patients randomized to intervention who are identified as having dropped out of care per the definition in section 1, the most recent physician in the specific patient's chain of care, will be given that patient's co-morbidity list via the CCE. This list will serve as a reminder that decisions for African-American patients have been different and will be designed to attenuate the subjective use of co-morbid states to justify decisions against lung resection surgery.

5. *Outcome Measures*

Primary Outcome. Whether or not patients undergo lung resection surgery represents the main study outcome. We will conform to the 4 month standard used in the SEER database. To ascertain the result, we will first call patients' physicians to determine whether surgery occurred within the designated time frame. Given the possibility that individual patients could seek other opinions and receive surgical care elsewhere, when appropriate, we will ask the patient, or a family member (if the patient is dead or unavailable), whether surgery was performed by someone other than the index physician. If surgery has not occurred, we will ask for reasons. Through appropriate consent, we will retain the option of confirmatory medical records review. For secondary analyses, we will record surgeries that occur beyond the 4 month threshold.

Secondary Outcomes.

1. One year, post-enrollment survival in surgical and non-surgical groups
2. Satisfaction of patients that received interventions compared to those who did not
3. Patients' perceptions of communication for those patients that received intervention compared to those who did not
4. SF-12 scores at baseline, 6 months post-enrollment and 12 months post enrollment

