We will analyze patient level cross-sectional dichotomous outcome data using logistic regression growth models. We will both limit analyses to the cancer communicator control group and do an all enrollee analysis by adding a communicator intervention / no communicator intervention predictor variable to the models. First, we will fit a saturated growth model to estimate annual proportions of these outcomes, before and after the registry/feedback intervention, to assess the effects of the intervention on these outcomes by contrasting the proportions before and after the interventions. We will test the null hypothesis that the proportions before and after the intervention are the same. We will repeat this analysis by including "race" and "race x time" interaction in this model to examine changes in these outcomes between the two races and also if there are any differential changes over time. We will test the null hypothesis that the proportions before and after the intervention are the same for each race

Data interpretation: If our data feedback / registry intervention is found to produce an effect in less than the 4 Cancer Centers, it will prompt further examination of the factors that moderate or mediate the relationship between the intervention and completion of cancer treatment. Thus, by conducting an embedded randomized cohort-control study of the Cancer Communicator intervention component, we may be better able to provide more information about the dimensions along which these interventions can or cannot be generalized.

hypothesis 2c. a cancer communicator who utilizes active listening and teach-back methods during discussions about lung cancer surgery with newly diagnosed, early stage patients will increase the rate of surgery in African-American patients more than Caucasian patients compared to usual care.

We will compare post intervention, unadjusted, surgical rates between African-American and White lung cancer patients using chi-square analysis as discussed under Aim 1. We will also perform the maximum rate analysis stratified by race. The regression models described above under Aim 1. We will also apply these analyses to patients in the communicator group alone selecting patients on an intention to treat basis.

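### Only African-American drop-outs in the communicator arm trigger a patient-specific physician reminder, so hypothesis 2c cannot credit a larger effect in African-American patients to active listening and teach-back alone

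*Protocol*

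**What the plan says.** Protocol section E.4.D (co-morbidity educational checklist) sets the trigger: "For African-American study patients randomized to intervention who are identified as having dropped out of care per the definition in section 1, the most recent" and continues "physician in the specific patient's chain of care, will be given that patient's co-morbidity list via the CCE". Its purpose is stated next: "This list will serve as a reminder that decisions for African-American patients have been different and will be designed to attenuate the subjective use" of co-morbidity as grounds for not operating. The list is therefore aimed at the primary outcome, surgery within 4 months. Section E.4.D cites section 1 for the drop-out definition, but the definition stands in E.4.A: no follow-up appointment within a month of the index visit, recommended surgery not scheduled, or a missed appointment.

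The other measures carry no race restriction:

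- Section E.4.A: "The CCE will re-engage any individual who is randomized to the patient intervention and who drops out of care". The CCE also tells the site physician champion about recommendations against surgery when the record shows no absolute contra-indication.
- Section E.4.B: drop-outs and negative recommendations are flagged in real time, and the champion arranges clinical review. Physician feedback goes to all sites because "cross-contamination for any physician-specific intervention is very likely".
- Section E, opening paragraph: the general checklist goes to all providers.

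SAP section 6, hypothesis 2c, names the agent as "a cancer communicator who utilizes active listening and teach-back methods during discussions about lung cancer surgery with newly diagnosed, early stage patients" and predicts that it "will increase the rate of surgery in African-American patients more than Caucasian patients compared to usual care". The stated analysis is: "We will compare post intervention, unadjusted, surgical rates between African-American and White lung cancer patients using chi-square analysis as discussed under Aim 1". It adds a maximum-rate analysis by race, a reference to the Aim 1 models and an analysis of the communicator group alone.

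**The concern.** Hypothesis 2c is about a difference between two arm effects: communicator against usual care in African-American patients, less the same contrast in White patients. The patient-specific list is delivered in just one of the four race-by-arm cells, so whatever it does to surgery falls entirely on that contrast. If communication worked equally well in both races and the list also worked, the trial would show a larger arm effect in African-American patients, and 2c as worded would credit it to communication technique.

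The attribution has a practical consequence. Under the closing paragraph of SAP section 6, significant benefit on surgical rates and disparities ends the study and starts training of the care teams in the communication methods. If part of a racial difference in effect came from the prompt to physicians, that training would omit an active component.

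**Working it through.** **1. What each cell receives**

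| Cell | CCE sessions and re-engagement | Real-time flags, champion review | General checklist to providers | Patient's own list to physician on drop-out |
|---|---|---|---|---|
| African-American, communicator | yes | yes | yes | **yes** |
| White, communicator | yes | yes | yes | no |
| African-American, usual care | no | flags and review not limited by race | yes | no |
| White, usual care | no | flags and review not limited by race | yes | no |

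The last column is non-zero in one cell only. It is therefore aliased with the race-by-arm contrast, and no model term can separate the two.

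**2. The plan's own figures.** SAP section 7 gives no sample size or power for 2c. It gives 80% power for one-sample tests against the previous study's rates. With two-sided alpha 0.05, power = Phi[(p1 - p0 - 1.96 x sqrt(p0(1 - p0)/n)) / sqrt(p1(1 - p1)/n)]:

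- n = 496, 0.63 to 0.69: (0.06 - 0.0425)/0.0208 = 0.84, power 0.800
- n = 159 (Black), 0.55 to 0.66: (0.11 - 0.0773)/0.0376 = 0.87, power 0.808
- n = 337 (White), 0.66 to 0.73: (0.07 - 0.0506)/0.0242 = 0.80, power 0.789

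These reproduce the stated 80%, but none addresses the 2c contrast.

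**3. Size of the distortion.** Let f be the share of African-American communicator-arm patients who drop out, and c the share of those who have surgery because of the list. With an equal communication effect in both races and no spillover, the race-by-arm difference that the list creates is f x c. Neither input is in the documents. Over assumed ranges, in percentage points:

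| f \ c | 10% | 25% | 50% |
|---|---|---|---|
| 10% | 1 | 2.5 | 5 |
| 20% | 2 | 5 | 10 |
| 30% | 3 | 7.5 | 15 |
| 45% | 4.5 | 11.25 | 22.5 |

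For scale, the Black and White gains used in SAP section 7 are 11 points (0.66 - 0.55) and 7 points (0.73 - 0.66), a difference of 4.

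**4. Spillover.** Suppose reminders also change decisions for other patients of the same physicians, by sA0 in African-American controls, sW1 in White communicator patients and sW0 in White controls. The contrast becomes f x c - sA0 - sW1 + sW0. If the two White terms are equal they cancel, leaving f x c - sA0, which is smaller than f x c. An upward distortion is likely but not certain.

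**5. Precision of the contrast.** Assume 1:1 allocation within race (159/2 = 79.5 and 337/2 = 168.5 per arm) and treat the SAP's before and after rates as the control and communicator rates:

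SE = sqrt(0.55 x 0.45/79.5 + 0.66 x 0.34/79.5 + 0.66 x 0.34/168.5 + 0.73 x 0.27/168.5) = sqrt(0.00311 + 0.00282 + 0.00133 + 0.00117) = 0.092

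The difference needed for 80% power is (1.96 + 0.84) x 0.092 = 0.26, or 26 points. A 4-point difference would be significant about 6% of the time. A 5-point artefact, with an equal 7-point communication effect in both races, would be significant about 8% of the time.

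**The case against.** The best case for the plan is that the list is part of the communicator arm. It is delivered by the CCE, follows from randomization, and supplements an arm that was never teach-back alone for either race, since the CCE also alerts the physician champion. Aim 3 openly describes a multi-modal intervention. What differs by race is only the list's increment over flagging, champion review and re-engagement, and that may be small. The contrast is also so imprecise that a formally significant false finding is unlikely unless the list has a large effect.

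Most of this stands, and it rules out several stronger conclusions that a reader might draw:

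- *That a larger effect could not be attributed to the communicator arm at all.* It can be attributed to the package as delivered. What is lost is attribution to active listening and teach-back.
- *That White drop-outs prompt no physician-side action.* Flagging and champion review are not limited by race.
- *That the randomized comparison fails.* Hypothesis 1a still compares the packages that the arms receive.
- *That the size follows from the previous study's 0.55 rate.* Applying conversion to the 45% without surgery gives 4.5 points for each 10% converted. But the trigger is dropping out, not lack of surgery at 4 months. A patient who attends every visit and is advised against surgery, or declines it, need not meet it. The calculation also assumes no spillover, contrary to E.4.B.

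The objection does not rescue the wording of 2c. Even read as a package, the package differs by race. A racial difference in arm effect is then not a difference in response to the same treatment, and 2c names only the communication technique. Section E.4.D and Aim 3 both list the checklist separately from the communicator. Aim 3 measures all elements together and does not isolate the list.

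**Conclusion.** The concern holds in limited form. Because the patient-specific list goes only to physicians of African-American communicator-arm drop-outs, a larger arm effect in African-American patients supports a claim about the communicator package including the race-targeted reminder. It does not support the claim in 2c about active listening and teach-back. This follows from the text and needs no numerical assumption.

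The size cannot be computed from the documents. It is f x c before spillover: 2 points at 20% and 10%, 5 points at 20% and 25%, and 1 to 22.5 points over the full assumed ranges. The problem concerns interpretation of a secondary contrast, not the validity of the main randomized comparison. The low precision for 2c makes a false significant result less likely, but it does not make the point estimate interpretable as an effect of communication.

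**What to change.** 1. Restate hypothesis 2c and its conclusion as the effect of *communicator plus race-targeted physician reminder*.
2. Record each list delivery with its date in the registry.
3. Report the number of lists delivered and the surgeries that follow, alongside the race-by-arm estimate.
4. If an analysis recodes surgeries after a delivery as no surgery, label it a conservative bound. It also removes surgeries due to CCE re-engagement in that cell, while equivalent surgeries in White patients still count. Spillover could also affect it.

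Using the same drop-out trigger for both races is an option for the sponsor, not a required change. It would alter a deliberately targeted disparity component and would still leave the list bundled with communication.

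The cost is one reworded hypothesis, one date field and a narrower claim. Items 1 to 3 change nothing that patients or physicians receive.

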Lung Cancer Surgery: Decisions Against Life Saving Care - The Intervention

NCT01687738

Protocol Date: May 13, 2011

Most Recent IRB Approval Date: March 29, 2016

Lung Cancer Surgery: Decisions Against Life Saving Care - The Intervention

STATISTICAL ANALYSES

Outcome Measures

Primary Outcome. Whether or not patients undergo lung resection surgery represents the main study outcome. We will conform to the 4 month standard used in the SEER database. To ascertain the result, we will first call patients' physicians to determine whether surgery occurred within the designated time frame. Given the possibility that individual patients could seek other opinions and receive surgical care elsewhere, when appropriate, we will ask the patient, or a family member (if the patient is dead or unavailable), whether surgery was performed by someone other than the index physician. If surgery has not occurred, we will ask for reasons. Through appropriate consent, we will retain the option of confirmatory medical records review. For secondary analyses, we will record surgeries that occur beyond the 4 month threshold.

Secondary Outcomes.

1. One year, post-enrollment survival in surgical and non-surgical groups
2. Satisfaction of patients that received interventions compared to those who did not
3. Patients' perceptions of communication for those patients that received intervention compared to those who did not
4. SF-12 scores at baseline, 6 months post-enrollment and 12 months post enrollment

6. Data Analysis:

Our current plan includes:

Descriptive statistics (means, standard deviations, frequencies, proportions, correlations, and graphical displays) will be computed for all study variables at baseline and post-baseline. The distribution of all outcome variables will be assessed to determine if distributional assumptions are valid. Descriptive statistics will be obtained for all the variables overall and by race and site. Statistical methods for addressing each of the specific aims of the study are detailed in this section. Since several statistical tests are planned, there is the possibility of incurring spurious results if we do not correct for multiple comparisons. All tests are based on a 2-sided alpha of 0.05.

The main outcome of interest is whether patients undergo surgery is a dichotomous variable, either yes or no. We will compute proportions to estimate the probability of surgery for blacks and whites and compute 95% confidence intervals for the proportions. Since the main outcome is dichotomous, logistic regression for clustered data (clustered within sites) using multiple predictors will be used to assess the simultaneous effect of predictors on the outcome.

Specific Aim 1. To maximize surgical rates for all patients with stage I and II, non-small cell lung cancer who do not have absolute contraindications for lung resection surgery.

hypothesis 1a. a cancer communicator who utilizes active listening and teach-back methods during discussions about lung cancer surgery with newly diagnosed, early stage patients will increase the rate of surgery in Caucasian and African-American patients who do not suffer absolute contra-indications for lung cancer surgery compared to usual care

The primary outcome variable, surgery yes or no, will be compared in the control group randomized to usual care, to the intervention group randomized to the cancer communicator. Bivariate analyses will be performed using the surgical outcome as the dependent variable. Independent variables in these analyses will include important group, demographic variables

such as age, race, marital status, household income, health insurance, gender, and education as well as measures of trust, patient satisfaction, functional status, self-reported health, comorbid illness, perceptions of communication, and the communication intervention. We will use bivariate analyses, including correlations and chi-square tests of association, to make preliminary assessments of the relationships between study variables, overall and by race.

The modeling approach will be to initially define as large a maximum model as possible using main effects only (initially no interactions). Preliminary analyses of similar data indicates that the sample size combined with a sufficient number of events (surgery yes) will allow upwards of 30-35 main effects to be included in the model with good reliability for estimation and inference. The generalized estimating equations (GEE) for binary outcomes will be used to fit logistic regression models for clustered data [102]. The primary outcome variable is binary, surgery yes or no, and outcomes of patients clustered within the same site (and/or MD) are expected to be correlated. GEE will allow fitting a logistic regression to the binary outcome while adjusting for the effect of clustering within the same site (and/or MD). As stated previously, independent variables in these analyses will include important demographic variables such as age, race, marital status, household income, health insurance, gender, and education as well as measures of trust, patient satisfaction, functional status, self-reported health, comorbid illness, perceptions of communication, and the communication intervention. The significance of each of the main effects while adjusting for all other effects from the maximum model will be assessed. A backwards elimination approach will, initially, remove effects with a p-value of greater than 0.10. This excludes selected predictors forced predictors into the model (forced predictors include group, comorbid illnesses and selected baseline scores). The reduced model will be refit. Variables have p-values greater than 0.05 will then be removed. The final reduced main effects model, including forced predictors will be refit. Selected interactions will be considered for inclusion into the final reduced main effects model. For the secondary outcomes, survival analysis techniques will be used to assess the one year, post-enrollment survival in surgical and non-surgical groups. Kaplan-Meier curves will be generated. Linear regression models for repeated measures (discrete) outcomes using GEE will be used to assess patient satisfaction of patients that received interventions compared to those who did not, for patients' perceptions of communication for those patients that received intervention compared to those who did not, and for SF12 scores at 6 months post-enrollment and 12 months post enrollment. Covariates will include baseline, group, and other covariates listed above.

hypothesis 1b. the communication intervention will be more effective in patients who score lower in measures of health literacy

Using the logistic regression analyses for clustered data as noted above, the interaction effects of health literacy, S-TOFHLA scores, and intervention group will be tested in all models. . S-TOFHLA scores will be tested as a continuous variable and also, separately, as a dichotomous variable comparing those categorized as inadequate or marginal literacy with those categorized as adequate literacy [103]. Cumulative pre-intervention surgical rates will be compared at all sites with post-intervention rates using Pearson's chi-square test. Post-intervention rates will be compared using test of proportions and changes in proportions from baseline will be compared between surgical and nonsurgical groups using appropriate methods. To determine if the post-intervention rate approaches maximal surgical rates, we will identify patients with high risk co-morbidities, above the age of 80, and need for pneumonectomy or multiple lobectomy in the "no surgery group", subtract this sum from the denominator then re-calculate the surgical rate. We will analyze the secondary specific aim, To measure the effect of the intervention on patients' perceptions of communication and satisfaction with care, by dichotomizing these variables and replacing surgery as the dependent variable in chi-square and logistic regression models as described under the specific aim above.

Specific Aim 2. To reduce the documented difference in lung resection surgery and mortality between African-American and White patients with early stage, non-small cell

lung cancer.

hypothesis 2a. giving physicians who make lung cancer surgery decisions data relating co-morbidity to surgical outcomes will reduce racial differences in surgery

hypothesis 2b. using a real time lung cancer registry to provide physicians race-specific feedback about their surgical treatment of early stage lung cancer patients will reduce racial differences in surgery

We will analyze patient level cross-sectional dichotomous outcome data using logistic regression growth models. We will both limit analyses to the cancer communicator control group and do an all enrollee analysis by adding a communicator intervention / no communicator intervention predictor variable to the models. First, we will fit a saturated growth model to estimate annual proportions of these outcomes, before and after the registry/feedback intervention, to assess the effects of the intervention on these outcomes by contrasting the proportions before and after the interventions. We will test the null hypothesis that the proportions before and after the intervention are the same. We will repeat this analysis by including "race" and "race x time" interaction in this model to examine changes in these outcomes between the two races and also if there are any differential changes over time. We will test the null hypothesis that the proportions before and after the intervention are the same for each race

Data interpretation: If our data feedback / registry intervention is found to produce an effect in less than the 4 Cancer Centers, it will prompt further examination of the factors that moderate or mediate the relationship between the intervention and completion of cancer treatment. Thus, by conducting an embedded randomized cohort-control study of the Cancer Communicator intervention component, we may be better able to provide more information about the dimensions along which these interventions can or cannot be generalized.

hypothesis 2c. a cancer communicator who utilizes active listening and teach-back methods during discussions about lung cancer surgery with newly diagnosed, early stage patients will increase the rate of surgery in African-American patients more than Caucasian patients compared to usual care.

We will compare post intervention, unadjusted, surgical rates between African-American and White lung cancer patients using chi-square analysis as discussed under Aim 1. We will also perform the maximum rate analysis stratified by race. The regression models described above under Aim 1. We will also apply these analyses to patients in the communicator group alone selecting patients on an intention to treat basis.

Specific Aim 3. To measure the effect of all elements of a multi-modal intervention that includes a cancer communication educator, data feedback, and a co-morbidity checklist on overall lung cancer surgery rates and rates for African-Americans.

To address specific Aim 3 we will first examine unadjusted relationships between race and clinical characteristics using chi-square analyses to obtain preliminary assessment of clinical characteristics that may be similar. A logistic regression model with binary outcome "undergo surgery or not undergo surgery" will be used to assess the effect of baseline scores, multiple clinical characteristics and patient race. Whether the effect of race remains constant across levels of clinical characteristics will be assessed in the logistic regression model using selected interaction terms of race x clinical characteristic. We will examine the direction and size of the interaction effects to help judge whether African-American patients undergo lung cancer surgery less often than Caucasian patients with similar clinical characteristics. We will repeat these analyses stratified by race to further examine predictors of differential effect. GEE with exchangeable correlation structure and generalized linear mixed models will be used to account for correlation within-physician. To measure the effect of the intervention, we'll examine before and after lung cancer surgery rates and control for the variables as noted in Specific Aim 1. To help control for the varying lengths of time before and after lung cancer surgery, we will include a length of time measure in our models as both a main effect and with selected interactions.

Specific Aim 4. To follow patients' functional status over time and explore the relationship of surgery, race, and co-morbid conditions on functional status.

hypothesis 4a. Individuals who undergo lung cancer surgery will experience better physical functioning at six months and 12 months than those who don't

hypothesis 4b. Individuals who undergo lung cancer surgery will experience better mental functioning at six months and 12 months than those who don't

The SF-12 physical and mental component scores will be converted to 0 – 100 scales and utilized as the dependent variable. Baseline scores will be compared first to 6 month scores then 12 month scores using paired t-tests. Generalized linear mixed models for repeated measures data will be constructed in a similar manner as the logistic regression models described above; however, surgical status, race, and comorbid conditions will be forced predictors in these model.

Note that interim analyses regarding specific aims 1 and 2 will be performed at the end of study year 2 then annually. If statistically significant benefits in care are documented on surgical rates and reduction in disparities, the study will be terminated and workshops and individual training sessions of the communication methodologies will be initiated for the care teams at all the study sites.

7. Sample Size

Power computations are computed for post-intervention comparison of proportions. The project anticipates enrolling 496 patients into the study due to constraints on budget, patient availability, and study duration. Thus, we compute the minimal effect size we can detect with statistical power of 80% for our primary aim, AIM 1, using the specified sample size. In computing the effect size, we specify our main outcome as the probability of undergoing surgery for all patients post-baseline as compared to the probability for all patients in the previous study because all groups will receive the data registry and feedback interventions.

Let p_1 be the proportion all patients who undergo surgery in the present study and $p_0 = 0.63$ be the proportion of patients who underwent surgery in the previous study. Using a one-sample test of proportion with 496 subjects overall and significance level of 0.05, we have 80% power to detect a minimally important difference (increase) in surgical rate of $p_0 = 0.63$ to $p_1 = 0.69$. With a sample size of 159 for blacks, we have 80% power to detect an overall increase from $p_0 = 0.55$ (as measured in the previous study) to $p_1 = 0.66$ with significance level of 0.05. With a sample size of 337 for whites, we have 80% power to detect an overall increase from $p_0 = 0.66$ (as measured in the previous study) to $p_1 = 0.73$ with significance level of 0.05.

From the analysis of our previous study, we found that practically negligible correlation existed between subjects for the primary outcome, surgery yes or no. The correlations seen ranged from -0.002 to 0.01 when using GEE for clustered observations in the previous study. In other words, clustering had a negligible effect on the results in the previous study. As such, we can expect the same in the proposed study. Therefore, we feel there is little or no need for power and sample size computation based on clustered observations. However, we will still adjust for patients clustering within site and/or physicians in the logistic regression models using GEE described in the Data Analysis section.
